 - Non-measurable bone-only disease. Non-measurable bone-only disease may include any of the following:
 - i. Blastic bone lesions (also known as sclerotic bone lesions)
 - ii. Lytic bone lesions without a measurable soft tissue component
 - iii. Mixed lytic-blastic bone lesions without a measurable soft tissue component
- 9. Have a Performance Status of 0 or 1 on the Eastern Cooperative Oncology Group scale (Oken et al. 1982)

10. Have adequate organ function as defined in table below

System	Laboratory Value
Renal	·
Serum creatinine or,	<1.5× ULN OR
Measured creatinine clearance or,	≥50 mL/min
Calculated creatinine clearance	(See Section 10.5 Appendix 5)
Hematologic	
ANC	$\geq 1.5 \times 10^{9}/L$
Platelets	$\geq 100 \times 10^{9}/L$
Hemoglobin	≥9 g/dL

Note: transfusions to increase a patient's hemoglobin level or initiation of erythropoietin or G-CSF therapy to meet enrollment criteria are not allowed in the 14 days preceding the first dose of study drug.

Hepatic	
	≤1.5× ULN
Total bilirubin	(Patients with Gilbert's syndrome with a total bilirubin ≤ 2.0 times ULN and
	direct bilirubin within normal limits are permitted.)
ALT and AST	≤3× ULN

Abbreviations: ALT = alanine aminotransferase; ANC = absolute neutrophil count; AST = aspartate aminotransferase; G-CSF = granulocyte colony stimulating factor; ULN = upper limit of normal.

- 11. Have discontinued previous therapies for cancer prior to receiving study drug, and recovered from the acute effects of therapy to at least Grade 1, except for residual alopecia and peripheral neuropathy, with the following therapy washout periods required prior to receiving study drug:
 - a. for myelosuppressive agents (for example, CDK4/6 inhibitors): at least 21 days
 - b. for nonmyelosuppressive agents (for example, Endocrine Therapy): 7 days or 5 half-lives, whichever is shorter
 - c. for investigational agents: 28 days or 5 half-lives, whichever is shorter
- 12. Patients must be able to swallow capsules/tablets
- 13. Are willing to participate for the duration of the study and to follow study procedures
- 14. Capable of giving signed informed consent as described in Section 10.1 Appendix 1, which includes compliance with the requirements and restrictions listed in the informed consent form (ICF) and in this protocol.

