Progressive Disease (PD): at least a 20% increase in the sum of the diameters of target lesions, taking as reference the smallest sum on study (including the baseline sum if that is the smallest). In addition to the relative increase of 20%, the sum must also demonstrate an absolute increase of at least 5 mm. The appearance of 1 or more new lesions is also considered progression.

For equivocal findings of progression (for example, very small and uncertain new lesions; cystic changes or necrosis in existing lesions), treatment may continue until the next scheduled assessment. If at the next scheduled assessment, progression is confirmed, the date of progression should be the earlier date when progression was suspected.

Stable Disease (SD): neither sufficient shrinkage to qualify for PR nor sufficient increase to qualify for PD, taking as reference the smallest sum diameters while on study.

Not Evaluable: when an incomplete radiologic assessment of target lesions is performed or there is a change in the method of measurement from baseline that impacts the ability to make a reliable evaluation of response.

Evaluation of Nontarget Lesions

Complete Response: disappearance of all nontarget lesions and normalization of tumor marker level. All lymph nodes must be non-pathological or normal in size (<10 mm short axis).

Non-CR/ non-PD: persistence of 1 or more nontarget lesions and/or maintenance of tumor marker level above the normal limits.

Progressive Disease: unequivocal progression of existing nontarget lesions. The appearance of 1 or more new lesions is also considered progression.

Not Evaluable: when a change in method of measurement from baseline occurs and impacts the ability to make a reliable evaluation of response.

Evaluation of Best Overall Response

The best overall response is the best response recorded from the start of the study treatment until the earliest of objective progression or start of new anticancer therapy, taking into account any requirement for confirmation. The patient's best overall response assignment will depend on the findings of both target and nontarget disease and will also take into consideration the appearance of new lesions. The Best Overall Response will be calculated via an algorithm using the assessment responses provided by the investigator over the course of the trial.

Time Point Response

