It is assumed that at each protocol-specified time point, a response assessment occurs (when no imaging/measurement is done at all at a particular time point, the patient is not evaluable (NE) at that time point). Table 1 provides a summary of the overall response status calculation at each time point for patients who have *measurable disease* at baseline.

Target Lesions	Non-Target Lesions	New Lesions	Overall Response
CR	CR	No	CR
CR	Non-CR/non-PD	No	PR
CR	Not evaluated	No	PR
PR	Non-PD or not all evaluated	No	PR
SD	Non-PD or not all evaluated	No	SD
Not all evaluated	Non-PD	No	NE
PD	Any	Yes or No	PD
Any	PD	Yes or No	PD
Any	Any	Yes	PD

Table 2: Time Point Response: Patients with Target (± Nontarget) Disease

Abbreviations: CR = complete response; NE = not evaluable; PD = progressive disease; PR = partial response; SD = stable disease.

Table 3 is to be used when patients have *nonmeasurable* disease only.

Nontarget Lesions	New Lesions	Overall Response	
CR	No	CR	
Non-CR/non-PD	No	Non-CR/non-PD ^a	
Not all evaluated	No	NE	
Unequivocal PD	Yes or No	PD	
Any	Yes	PD	

Table 3: Time Point Response: Patients with Nontarget Disease Only

Abbreviations: CR = complete response; NE = not evaluable; PD = progressive disease.

^a non-CR/non-PD is preferred over SD for nontarget disease.

Frequency of Tumor Reevaluation

A baseline tumor evaluation must be performed within 4 weeks before patient begins study treatment. Frequency of tumor reevaluation while on and adapted to treatment should be protocol specific and adapted to the type and schedule of treatment. In the context of Phase 2 studies where the beneficial effect therapy is not known, follow-up every 6-8 weeks is reasonable. Normally, all target and non-target sites are evaluated at each assessment using the same method. However, bone scans may need to be repeated only when CR is identified in target disease or when progression in bone is suspected.

Confirmatory Measurement/Duration of Response

Confirmation

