4.4.2. Supportive Secondary Endpoints

All supportive secondary endpoint analyses will be conducted for each comparison (Arm A versus Arm B, and Arm C versus Arm A) per the prespecified analysis population for each comparison.

Objective response rate (ORR) is defined as the proportion of participants who achieve a confirmed best overall response of CR or PR. The ORR with 95% CI will be summarized for each treatment arm and compared between treatment arms using the Cochran-Mantel-Haenszel test adjusting for the randomization strata. The analysis of ORR will be conducted in the ORR evaluable population. The Mantel-Haenszel estimate of the common risk difference of ORR with 95% CI between 2 arms will also be estimated.

Clinical benefit rate (CBR) is defined as the number of participants who achieve a best overall response of CR, PR, or SD \geq 24 weeks divided by the total number of participants randomized to the corresponding treatment arm. The CBR with 95% CI will be summarized for each treatment arm and compared between treatment arms using the Cochran-Mantel-Haenszel test adjusting for the randomization strata. The Mantel-Haenszel estimate of the common risk difference of CBR with 95% CI between 2 arms will also be estimated.

Duration of response (DoR) is defined as the time from the date measurement criteria for CR or PR (whichever is first recorded) are first met until the first date that disease is recurrent or objective progression is observed, per RECIST 1.1 criteria, or the date of death from any cause

in the absence of objectively determined disease progression or recurrence. The DoR will be censored according to the same scheme as the main scheme for PFS. Median DoR with 95% CI and curves for each treatment arm will be estimated using the Kaplan-Meier method. The analysis of DoR will be based on the participants who achieve an objective response (CR or PR).

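### As written, the clinical benefit rate gives no credit for non-CR/non-PD lasting 24 weeks, so durably controlled bone-only patients count as failures

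*SAP*

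**What the plan says.** **Numerator.** SAP 4.4.2 counts the "number of participants who achieve a best overall response of CR, PR, or SD" of at least 24 weeks. Protocol 9.4.3.3 uses the same definition.

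**Denominator.** The count is "divided by the total number of participants randomized to the corresponding treatment arm". There is no restriction to measurable disease. ORR, in the same SAP section, is handled differently: "The analysis of ORR will be conducted in the ORR evaluable population", which means measurable disease at baseline.

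**Eligibility.** Inclusion criterion 8 (Protocol 5.1) requires either measurable disease or non-measurable bone-only disease. On the latter it says: "Non-measurable bone-only disease may include any of the following", and lists blastic, lytic and mixed lesions without a measurable soft-tissue component. Patients with nontarget disease only are therefore, in practice, the bone-only patients.

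**Response categories.** Protocol Appendix 3, Table 3 ("Time Point Response: Patients with Nontarget Disease Only") has four outcomes: CR, non-CR/non-PD, NE and PD. Its footnote reads: "non-CR/non-PD is preferred over SD for nontarget disease". Appendix 3 defines SD under target lesions as "neither sufficient shrinkage to qualify for PR nor sufficient increase to qualify for PD, taking as reference the smallest sum diameters while on study".

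**Best overall response.** Appendix 3 states: "The Best Overall Response will be calculated via an algorithm using the assessment responses provided by the investigator over the course of the trial". Neither document sets out that algorithm in enough detail to show what it does with non-CR/non-PD.

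**The concern.** The CBR numerator uses the response vocabulary for patients with target lesions, while its denominator includes patients who are scored with a different vocabulary. For a bone-only patient, lasting absence of progression is what CBR is meant to capture, yet the label given to that state is not on the list of successes.

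CBR is a listed secondary efficacy endpoint. It gets a Cochran-Mantel-Haenszel test, a Mantel-Haenszel risk difference with 95% CI, and a parallel BIRC summary. If the rule is programmed as written, reported disease control is too low in every arm. If the investigator and BIRC data sets handle the label differently, the two CBRs are not comparable.

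The plan deals with bone-only disease elsewhere. It restricts ORR to measurable disease, sets bone-only progression criteria for PFS (Protocol 8.1.3), and plans a bone-only subgroup (SAP 4.8.12). The gap in CBR therefore looks like an oversight rather than a choice.

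**Working it through.** **Step 1: trace one patient through the rules.** Take a bone-only patient with no progression for a year and no disappearance of all lesions.

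- Each scan is non-CR/non-PD under Table 3. There is no PR or SD row.
- The SD definition cannot be applied, because it refers to a sum of target-lesion diameters and this patient has no target lesions.
- No sentence in either document converts non-CR/non-PD to SD when best overall response is derived.
- The patient is in the denominator and not in the numerator.

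The remaining routes into the numerator are CR of all nontarget lesions, or an SD recorded by the site despite the footnote.

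**Step 2: size of the understatement.** Let f be the bone-only share, p the proportion of those patients controlled at 24 weeks, and c their CR rate.

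Understatement per arm = f × (p − c).

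The documents give none of the three. With c = 0 and assumed ranges f = 15 to 25% and p = 40 to 60%:

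- low end: 0.15 × 0.40 = 6.0 points
- high end: 0.25 × 0.60 = 15.0 points

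**Step 3: is the assumed control rate compatible with the plan?** The plan states no expected CBR, so there is no CBR figure to reproduce. The PFS assumptions in SAP Section 5 give an anchor: Arm B median 4.3 months, hazard ratio 0.74, exponential survival. These inputs do reproduce the plan's own figures:

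- Power = Φ(½√480 × |ln 0.74| − z), which gives 76.5% at one-sided 0.005 and 91.0% at 0.025, against the stated at least 76% and at least 91%.
- Median gain = 4.3/0.74 − 4.3 = 1.5 months, as stated.

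Twenty-four weeks is 168/30.4375 = 5.52 months. Progression-free probability at that point:

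- Arm B: 0.5^(5.52/4.3) = 41.1%
- Arm A: 0.5^(5.52 × 0.74/4.3) = 51.8%

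Both lie inside 40 to 60%. With f = 15 to 25% and c = 0, the understatement is 6.2 to 10.3 points in Arm B and 7.8 to 12.9 in Arm A. This treats bone-only patients as having the same PFS as everyone else, which is an assumption.

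**Step 4: the between-arm difference.** Let d be the true arm difference in 24-week control among bone-only patients, and Δc the arm difference in their CR rates. The absolute CBR difference changes by f × (d − Δc). If d and Δc are both zero, nothing changes. If instead bone-only patients benefit as much as the rest, and c = 0, the difference is multiplied by (1 − f). Using the Step 3 rates, 320 per arm and a one-sided 0.025 unstratified two-proportion test:

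| f (assumed) | Bone-only per arm | CBR, Arm B | CBR, Arm A | Difference (points) | Nominal power |
|---|---|---|---|---|---|
| 0 (or rule corrected) | – | 41.1% | 51.8% | 10.7 | 78% |
| 10% | 32 | 37.0% | 46.6% | 9.6 | 70% |
| 20% | 64 | 32.9% | 41.4% | 8.6 | 61% |
| 30% | 96 | 28.8% | 36.2% | 7.5 | 52% |

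Setting c at 5% in both arms leaves the differences as shown and moves power by at most about one point. The power column only illustrates lost precision; the plan makes no power claim for CBR.

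**The case against.** **The footnote is a preference, not a ban, and the algorithm is unseen.** A reader might infer that SD can never be assigned to a bone-only patient. The documents do not go that far. A site may record SD, and the programmed derivation may map non-CR/non-PD to it. This stands as a limit on certainty: the result follows from the text, not from a demonstrated scoring error. It does not remove the point, because neither document states such a mapping and the written rules lead the other way.

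**SD may be shorthand.** The PFS censoring footnote in SAP 4.3.2 also lists adequate assessments as CR, PR, SD or PD. Taken literally, a non-CR/non-PD scan would then not be adequate, which sits badly with bone-only progression criteria and a bone-only PFS subgroup. Loose use of SD throughout is plausible. It remains an inference, and it is a reason to write the mapping down. The footnote is a separate matter: amending it alone leaves the CBR numerator unchanged.

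**Dilution and imbalance.** A reader might infer that the treatment difference is necessarily diluted. Step 4 shows that this needs a treatment effect on control in bone-only patients. A reader might also infer that chance imbalance in bone-only disease would distort the comparison freely. Bone-only status is not a stratification factor, but visceral metastasis is, bone-only patients fall in the non-visceral stratum, and the CMH test adjusts for the randomization strata. Imbalance is therefore partly contained.

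**Importance.** SAP 4.4.2 labels these endpoints supportive, and Protocol 9.4.3.2 says that secondary endpoints other than OS are not error controlled. No alpha, sample size or stopping rule depends on CBR. That stands in full.

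**Conclusion.** The point holds as a defect in the written definition. Followed literally, bone-only patients controlled for at least 24 weeks are CBR failures unless they reach CR or a site records SD against the stated preference.

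The understatement is about the bone-only share times the 24-week control rate in those patients: 6 to 15 points per arm under the assumed 15 to 25% share, 40 to 60% control and no bone-only CRs. The control range is compatible with the plan's PFS assumptions; the share has no source in the documents. Loss in the between-arm difference is conditional on a treatment effect in bone-only patients.

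The documents do not support reading this as a threat to the trial's main conclusions. It affects the reported level, and possibly the contrast, of one supportive endpoint. It should be corrected because the written rule gives a wrong answer for an eligible group and correction is nearly free.

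**What to change.** In SAP 4.4.2 and Protocol 9.4.3.3, define CBR as best overall response of CR or PR, or SD or non-CR/non-PD lasting at least 24 weeks, over all participants randomized to the arm. Apply the same rule to CBR by BIRC.

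The cost is one line in each document and a matching programming rule; no new data are needed. If the best-overall-response algorithm already makes this mapping, the change only documents it. The rule should be fixed before unblinded comparative results are seen, so that it cannot appear to have been chosen after the fact.

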6.3. Measures to Minimize Bias: Randomization and Blinding

This is a randomized, open-label study. The route of administration for the anti-cancer agents in the study justifies an open-label design. Upon obtaining informed consent, site personnel should

access the IWRS, which will assign a patient number. Participants who meet all criteria for enrollment will be randomly assigned to the treatment arm. Assignment to treatment groups will be determined by a computer-generated random sequence using the IWRS. Sites will be prompted to enter the specific Arm B ET of choice at time of randomization until the enrollment to Arm B is stopped. Each participant in this study will be aware of his or her own assigned treatment group. At each investigative site, all staff involved in treating and caring for study participants will have full knowledge of treatment assignments for the participants under their care.

In order to maintain the scientific integrity of the trial, access to study data will be strictly controlled prior to the interim and final analyses. Access to the EDC will be limited to those who require this information for their role and all access will be documented.

For the accumulated aggregate database to which Sponsor statisticians (or those of its designee) have access, treatment assignment, and other parameters that can disclose treatment assignment will be scrambled or masked. Therefore, the Sponsor and all investigative sites will remain blinded to treatment group assignments for the aggregate database until the database lock for the final analysis. Scrambled treatment assignments will be used in the reporting database until the study reaches its final analysis or the study is determined to be positive or futile by the DMC. During this time, analyses using unblinded treatment codes will be performed only at the interim analysis points specified in the protocol/SAP.

Participants will be randomized 1:1:1 between the 3 treatment arms, of either imlunestrant (Arm A), Investigator's Choice Endocrine Therapy (Arm B), or imlunestrant plus abemaciclib (Arm C), using the following stratification factors:

- previous treatment with any CDK4/6 inhibitor (yes versus no)
- presence of visceral metastases (yes versus no); visceral includes lung, liver, brain, pleural, and peritoneal involvement, and
- region (East Asia versus North America/Western Europe versus Others).

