9.4.3.3. Other Secondary Analyses

All other secondary analyses will be conducted for each comparison (Arm A versus Arm B in the ITT and *ESR1*-mutation detected populations and Arm C versus Arm A in the ITT population) per the prespecified analysis populations.

Objective response rate (ORR) is defined as the number of participants who achieve a confirmed best overall response of CR or PR divided by the total number of participants randomized to the corresponding treatment arm. The ORR with 95% CIs will be summarized for each treatment arm and compared between treatment arms using the Cochran-Mantel-Haenszel test adjusting for the randomization strata. The analysis of ORR will be conducted in the ORR evaluable population, which is defined as all randomized participants who have measurable disease per RECIST v1.1 at baseline.

Clinical benefit rate (CBR) is defined as the number of participants who achieve a best overall response of CR, PR, or SD \geq 24 weeks divided by the total number of participants randomized to the corresponding treatment arm. The CBR with 95% CIs will be summarized for each treatment arm and compared between treatment arms using the Cochran-Mantel-Haenszel test adjusting for the randomization strata.

Duration of response (DoR) is defined as the time from the date measurement criteria for CR or PR (whichever is first recorded) are first met until the first date that disease is recurrent or objective progression is observed, per RECIST 1.1 criteria, or the date of death from any cause in the absence of objectively determined disease progression or recurrence. The DoR will be censored according to the same rules as PFS. Median DoR with 95% CI and curves for each treatment arm will be estimated using the Kaplan-Meier method. The analysis of DoR will be based on participants who achieve an objective response (CR or PR).

Progression-free survival by blinded independent review committee (BIRC) is defined the same way as the primary endpoint of PFS. For BIRC analysis, scans will be collected and reviewed in all randomized participants based on RECIST version 1.1. PFS as assessed by BIRC intends to evaluate the reliability of the treatment effect based on the investigator-assessed PFS. PFS as assessed by BIRC will be analyzed using the same methods as the investigator-assessed PFS. The evaluation for the potential bias in the investigator assessment will also be performed. Further details will be described in the SAP.

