Progression-free survival by blinded independent review committee (BIRC) is defined the same way as the primary endpoint of PFS. For BIRC analysis, scans will be collected and reviewed in all randomized participants based on RECIST version 1.1. PFS as assessed by BIRC intends to evaluate the reliability of the treatment effect based on the investigator-assessed PFS. PFS as assessed by BIRC will be analyzed using the same methods as the investigator-assessed PFS. PFS as assessed by BIRC is not intended to provide an alternative means of definitive analysis, but it may be useful to evaluate bias in local assessments. Discordance rates (i.e., differences in assessment of progression between investigator and BIRC) will be summarized for each arm (Amit, et al. 2011). Specifically, differential discordance will be described using early discrepancy rate and late discrepancy rate differences.

	BIRC					
Investigator	PD	No PD				
Investigator PD	a=a1+a2+a3	b				
No PD	С	d				

BIRC-Assessed Versus Investigator-Assessed Disease Progression

Abbreviations: PD = progressive disease; BIRC = blinded independent review committee.

al: number of agreements on timing and occurrence of PD.

a2: number of times investigators declare PD later than BIRC.

a3: number of times investigators declare PD earlier than BIRC.

The early discrepancy rate (EDR) quantifies the frequency with which the investigator assessment declares progression early relative to BIRC within each arm and is defined as:

EDR = (b+a3)/(a+b)

The late discrepancy rate (LDR) quantifies the frequency with which the investigator assessment declares progression later than BIRC within each arm and is defined as:

LDR = (c+a2)/(b+c+a2+a3)

The EDR and LDR will be summarized for each treatment arm and the differential discordance around each measure can be defined as the rate on the experimental arm minus the rate on the control arm. A negative differential discordance for the EDR and/or positive differential discordance for the LDR are suggestive of a bias in the investigator-assessed PFS favoring the experimental arm.

The ORR, CBR, and DoR by BIRC will also be summarized for each arm.

Adverse Events

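### SAP 4.4.2 reads the sign alone of two discordance differences as a hint of investigator bias, a criterion that unbiased readers would meet more often than not

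*SAP*

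**What the plan says.** All three primary endpoints are investigator-assessed PFS (SAP 1.1), and Protocol 6.3 states "This is a randomized, open-label study". Protocol 9.4.3.3 promises that "The evaluation for the potential bias in the investigator assessment will also be performed" and leaves the detail to the SAP.

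SAP 4.4.2 cross-classifies progression calls within each arm:

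- a: both readers call progression (a1 same timing, a2 investigator later, a3 investigator earlier)
- b: investigator only
- c: BIRC only
- d: neither

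It sets EDR = (b + a3)/(a + b) and LDR = (c + a2)/(b + c + a2 + a3). Between arms, "the differential discordance around each measure can be defined as the rate on the experimental arm minus the rate on the control arm". The reading given is that "A negative differential discordance for the EDR and/or positive differential discordance for the LDR are suggestive of a bias in the investigator-assessed PFS", towards the experimental arm.

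The same section says "differential discordance will be described using early discrepancy rate and late discrepancy rate differences". It also plans BIRC PFS in everyone randomized: "PFS as assessed by BIRC will be analyzed using the same methods as the investigator-assessed PFS". On its role, the SAP says: "PFS as assessed by BIRC is not intended to provide an alternative means of definitive analysis, but it may be useful to evaluate bias".

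No interval, margin or test is given for the EDR and LDR differences. By contrast, the ORR and CBR risk differences in that section each get a 95% CI. SAP 4.1 sets the level of the intervals that are reported, but does not say that these differences receive one.

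**The concern.** A difference of two estimated proportions is almost never exactly zero. With no differential reading, each sign is close to a coin toss, and accepting either of two signs raises the chance above one half. Taken as written, the sentence would lead the study report of a sound trial to describe its discordance as suggestive of bias more often than not. The same words would cover a chance gap of half a point and a distortion of ten points. This is the only reading rule the SAP states for the discordance measures, and it has no rule for setting BIRC PFS against investigator PFS.

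**Working it through.** **1. The plan's own figures.** The documents give no operating characteristic for this criterion and no discordance rates. What they fix is size: about 320 in each of Arms A and B, 220 in Arm C, about 240 in the ESR1-mutation subset (120 per arm), and 480 events among 640 (75%). The H1 power that goes with these reproduces: √(480/4) × |ln 0.74| − 2.576 = 10.954 × 0.3011 − 2.576 = 0.72, and Φ(0.72) ≈ 0.765, against the stated figure of at least 76%. All discordance rates below are assumptions.

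**2. Why the rate exceeds one half.** Let r be the correlation between the two differences with the sign reversed. For two centred normal differences,

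P(either sign) = 3/4 − arcsin(r)/(2π).

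The counts b and a3 raise EDR and lower LDR, so r is positive and the two signs tend to occur together. The union is still above 0.5 for any r below 1: 0.67 at r = 0.5, 0.60 at r = 0.8, 0.57 at r = 0.9.

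**3. One worked case, identical arms of 320.** Assume investigator progression in 75% (240), b = 20% of those (48), a = 192, same timing in 65% of a with the rest split evenly (a2 = a3 = 33.6), and c = 10% of the other 80 (8).

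- EDR = (48 + 33.6)/240 = 0.340
- LDR = (8 + 33.6)/(48 + 8 + 33.6 + 33.6) = 41.6/123.2 = 0.338
- SD of EDR difference ≈ √(2 × 0.34 × 0.66/240) = 0.043
- SD of LDR difference ≈ √(2 × 0.338 × 0.662/123.2) = 0.060
- Simulated: P(EDR difference < 0) = 0.498, P(LDR difference > 0) = 0.496, both 0.364, so either = 0.498 + 0.496 − 0.364 = 0.63. The formula with r = 0.667 gives 0.634.

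**4. Range with unbiased readers.** The multinomial grid had 648 settings (120, 220 or 320 per arm; investigator progression 65-75%; same timing 50-80% of a; a2 share 30-70%; b 10-30%; c 5-40%). Two scan-based models used the protocol's 8-week then 12-week imaging. Their assumed per-scan false-progression rates were 2-8% and missed-progression rates 15-30%, the same for both readers and both arms.

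| Model | Treatment effect | Criterion met |
|---|---|---|
| Multinomial grid | none | 57-69%, median 63% |
| Scan model 1, A vs B | none | 60-62% |
| Scan model 1, A vs B | HR 0.74 | 51-53% |
| Scan model 2, three comparisons | none | 58-62% |
| Scan model 2, three comparisons | HR 0.74, 0.57, 0.70 | 51-55% |

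The grid median is the same at all three arm sizes, so a larger trial would not help. The rate falls when the drug works because a true effect alone moves the EDR difference upward: 2-3 points in scan model 1, and roughly 1 to 5 points across comparisons and settings.

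**5. What a met or unmet criterion tells the reader.** Assume a real bias of 3 points more false early calls per scan in control and 15 points more missed progressions in the experimental arm. At the design hazard ratios the criterion is then met in 94-100% of trials, against 52-55% with no bias in the same runs. Meeting it multiplies the odds of that bias by only about 94/55 = 1.7 to 100/52 = 1.9. Not meeting it occurs in 0-6% against 45-48%, a factor of at most about 6/45 = 0.13.

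**6. Alternatives with no bias.** Requiring both signs is still met in 31-42%. Requiring a difference beyond 1.96 standard errors in the bias direction is met in about 3-5%. The missing interval or margin therefore matters more than the conjunction.

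**The case against.** The strongest reply is that this is not a decision rule. The SAP describes the differences, calls a direction suggestive, and attaches no action or claim. Each arm's EDR and LDR will be shown, so a trivial gap will not look like a large one. That stands, and it limits the point to how one sentence would be read.

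A reader might infer more: that the report could not tell anyone whether the primary hazard ratios are reliable. The documents do not support that. BIRC PFS is planned in all randomized participants with the stratified log-rank test and a hazard ratio with 95% CI, so a blinded estimate will stand beside each investigator estimate.

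A reader might also infer that the criterion is uninformative in both directions. It is not: step 5 shows that an unmet criterion argues against a large bias. It works as a sensitive, unspecific screen.

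A third tempting step is to call bias only when the 95% CI excludes zero. At the design hazard ratios that rule detects the assumed bias in 80-92% of trials for A vs B in the ITT population and 61-79% for C vs A, but only 36-49% in the ESR1 subset, which carries 0.02 of the 0.025 alpha. With half that bias, detection in the subset falls to 13-18%. Zero is also not a neutral reference when the drug works (step 4), and the shift favours the sponsor.

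The SAP cites a published meta-analysis for the method. Whether it offers thresholds cannot be seen here, and none is carried into the plan.

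**Conclusion.** The point holds for the sign-only reading. With unbiased readers the criterion is met in about 57-69% of trials with no treatment effect and about 51-55% at the design hazard ratios. No single figure can be derived from the documents, since the discordance rates, reader error rates and follow-up pattern are all assumed. The conclusion that it is met more often than not held in every unbiased setting tried. A met criterion is weak evidence by itself. An unmet one is informative against a large bias. The analysis is descriptive and supportive, BIRC PFS is the fuller check, and no primary inference changes.

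**What to change.** Replace the sign-only sentence in SAP 4.4.2 with:

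> Differential EDR and LDR will be reported with two-sided 95% CIs (bootstrap within arm) for each comparison. The direction, size and CI, including the limit in the unfavourable direction (lower for EDR, upper for LDR), will be interpreted together with the BIRC versus investigator PFS hazard ratios. The sign of a difference alone will not be read as evidence of bias, and a CI that includes 0 will not be read as absence of bias.

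Do not make exclusion of zero by the CI the sole criterion, given its low sensitivity in the ESR1 subset and the upward shift of the EDR difference under a true effect.

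The cost is a bootstrap on counts already planned, with no new data, readers or participants. The intervals will be wide in the ESR1 subset. With grid-median SDs of 7.3 and 9.7 points at 120 per arm, the half-widths are about 1.96 × 7.3 = 14 points for EDR and 1.96 × 9.7 = 19 points for LDR. Showing that width tells readers how much differential discordance remains possible.
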